6.8.4 Prioritization of Lesions for Injection

- It is strongly recommended that baseline lesion selection and the prioritization of lesions for injection are discussed on an ongoing basis with the multidisciplinary care team.
- Prioritization of lesions for injection should favor larger lesions over smaller lesions and symptomatic lesions over asymptomatic lesions.
- Dosing of SL-172154 will proceed using a flat dose and fixed volume format (see Section 3.4 for additional details). The entire drug dose must be instilled into one to three tumor lesions at a given ITI time point in order to ensure that the toxicity assessment can be accurately ascribed to a specific drug dosage. A maximum of three lesions can be injected at any dosing time point.

- If multiple lesions are being injected at a given time point, the drug product should be split between the lesions based on the relative size of each lesion. A minimum of 0.5 mL of SL-172154 should be instilled into any given lesion.
- Dosing may continue as per the specified interval until all clinically feasible lesions are injected at least once and then lesions that were previously injected may be re-injected.
- A previously injected lesion that is stable or responding may be re-injected until the lesion has completely resolved or as long as clinically feasible. At the time of complete resolution of a lesion, no further injections should be administered into the lesion with the complete resolution, however other lesions can be injected if clinically feasible.
- A previously injected lesion that is progressing may be re-injected if the benefit-risk ratio of continuing therapy is justified and all criteria for re-injection are met.
- New lesions that develop during the study which meet all of the criteria for being injectable, may be considered for injection.

6.8.5 Documentation of Intratumoral Injections

- At baseline, all lesions that are selected for ITI must be recorded via digital photography or by image-based documentation (if using ultrasound). Photographs should include a close-up view of the index lesion and an anatomical location view of the index lesion area(s). Two exposures for each location and lesion will be taken. **Refer to the Site Imaging Manual for complete instructions.**
- All lesions undergoing ITI must be documented. Documentation of the needle tip on or within the lesion at the time of injection will be obtained either by digital photography or image-based documentation. For ultrasound guided injections, all relevant treatment planning radiological images (e.g., needle in lesion images, ultrasound images clearly marking the lesion to be injected) may be centrally collected and should be made available to the Sponsor or designated central imaging vendor, for collection, storage, and possible future central re-analysis. These images will be used to confirm the lesions that were injected vs non-injected in order to assess the local and anesthetic or bystander response to therapy.

6.9 Unscheduled Visit

In the event of an unscheduled visit, the subject should undergo safety screening to include a physical exam, vital signs (HR, BP, T, and RR) and pulse oximetry. Clinical hematology and chemistry labs may be collected if considered necessary for subject assessment. All AEs or SAEs reported by the subject or observed by the investigator should be documented and reported; this includes relevant medical information gathered during the unscheduled visit related to clinical assessment of AEs or SAEs (Section [7.4](#)).

7. SAFETY ASSESSMENTS

Subjects will be followed continuously for all AEs starting when a subject has signed the ICF, throughout the course of treatment and for 90 days after the last dose of IP. After a subject is discontinued from SL-172154 due to PD or for other reasons, any ongoing AEs should be followed until resolution (or return to baseline) and documented in the eCRF. If another anti-cancer agent is started within 90 days after the last dose of SL-172154, only SAEs and AEs that occur prior to starting the new anticancer therapy should be recorded. All observed or volunteered AEs (serious

or non-serious) and abnormal laboratory test findings, if applicable, whether suspected to have a causal relationship to SL-172154 study therapy or not will be recorded in the subject medical record and in the eCRF. AEs will be graded according to NCI-CTCAE v5.0. For all AEs, sufficient information will be pursued and/or obtained to permit an adequate determination of seriousness and outcome of the event (i.e., whether it should be classified as a SAE or not) and an assessment of the causal relationship between the AE and SL-172154/study therapy. AEs will be followed until resolution (or return to baseline) or stabilization. Refer to Section [7.4](#) for documentation and reporting of AEs.

7.1 Definitions for Safety Parameters

Event	Definition
Adverse Event (AE)	
The observation period of an AE starts at the time of signing informed consent and includes baseline or washout periods, even if no study treatment has been administered.
 
The definition of an AE is any untoward medical occurrence in a subject to whom the IP, has been administered, regardless of whether the event is considered related to that product. An AE is also an undesirable medical condition due to a study-related procedure.

Adverse Reaction (AR)	AR is an untoward and unintended response in a subject to an IP (SL-172154). A causal relationship between a trial medication and an AE is at least a reasonable possibility, i.e. the relationship cannot be ruled out.
Serious Adverse Event (SAE) or Serious Adverse Reaction (SAR)	
An AE or suspected AR that is considered "serious" if, in the view of either the investigator or Sponsor, it results in any of the following outcomes:
 
 • Death (Note: death is an outcome not an event) • A life-threatening AE (an event in which the subject was at risk of death at the time of the event; it does not refer to an event which hypothetically might have caused death if it were more severe) • Inpatient hospitalization or prolongation of existing hospitalization • A persistent or significant incapacity or substantial disruption of the ability to conduct normal life functions • A congenital anomaly/birth defect. • Important medical events that may not result in death, be life-threatening, or require hospitalization may be considered serious when, based upon appropriate medical judgment, they may jeopardize the participant and may require medical or surgical intervention to prevent one of the outcomes listed in this definition. Examples of such medical events include allergic bronchospasm requiring intensive treatment in an emergency room or at home, blood dyscrasias or convulsions that do not result in inpatient hospitalization, or the development of drug dependency or drug abuse.

Event	Definition
Laboratory test(s) that meet definition of an AE or SAE:	
 Any laboratory test result that meets the definition of an AE or SAE or requires holding or discontinuation of IP; or requires corrective therapy, must be documented appropriately. Ad hoc labs should be collected as noted in Section 6.3.6.3 above if injection-related reaction/CRS or an irSAE occurs. 
The investigator must review the laboratory report, document this review, and record any clinically relevant changes occurring during the study in the subject's medical record and recorded in the AE section of the eCRF. The laboratory reports must be filed with the source documents. Clinically significant abnormal laboratory findings are those which are not associated with the underlying disease, unless judged by the investigator to be more severe than expected for the participant's condition.
 
All laboratory tests with clinically significant abnormal values during participation in the study should be repeated until the values return to normal or baseline or are no longer considered clinically significant by the investigator.
 
If such values do not return to normal/baseline within a period judged reasonable by the investigator, the etiology should be identified, and the Sponsor notified.
 
If laboratory values from non-protocol specified laboratory assessments performed at the institution's local laboratory require a change in subject management or are considered clinically significant by the investigator (e.g., AE, SAE or dose interruption), then the results must be recorded in the eCRF.

Unexpected Adverse Reaction	An AR (causality related Adverse Event), the nature, severity or outcome of which is not consistent with the reference safety information section of the SL-172154 IB. Product reference safety information is contained in the current Guidance for Investigators in Section 6.0 of the Investigator's Brochure provided to the Investigator by the Sponsor.
Suspected Unexpected Serious Adverse Reaction (SUSAR)	Suspected Adverse Reaction (causality related AE) that is serious and unexpected.

7.1.1 Events not Qualifying as AEs/SAEs

Because attribution of AEs is difficult in a phase 1 study, any toxicity experienced by subjects in this study should be recorded as AEs unless otherwise specified. The following are not considered to be AEs or SAEs:

- Medical or surgical procedures (e.g., endoscopy, appendectomy). The condition that leads to the procedure is considered the AE.
- Elective procedures, planned hospitalizations, and procedures for treatment of conditions noted in the subject's medical history (present prior to signing the ICF) that have not worsened are not considered AEs.

- Situations where an untoward medical occurrence did not occur (i.e., admission to hospital for social circumstances).
- Anticipated day-to-day fluctuations of pre-existing medical conditions that were present at start of study. These conditions are considered part of the subject's medical history and must be adequately documented on the appropriate page of the CRF.
- Clear progression of disease under study should not be reported as an AE or SAE (unless the investigator considers the progression of underlying neoplasia to be atypical in its nature, presentation or severity from the normal course of the disease in a particular subject). Findings that are clearly consistent with the expected progression of the underlying cancer should not be reported as an adverse event, and hospitalizations due to the progression of cancer do not necessarily qualify for an SAE.
- In the case where the medical condition is known when the participant enters the trial, only worsening (increased frequency or intensity of the episodes or attacks) will be documented as an AE. If the disease is detected during the trial, and if repeated episodes enable diagnosis of a chronic disease, the episodes will be grouped together in the CRF, and the diagnosis will be clearly described.
- Laboratory abnormalities: An isolated, out-of-range laboratory result in the absence of any associated, clinical finding may or may not be considered an AE; the Investigator's evaluation should be based on a consideration of the overall clinical context.

7.2 Classification of an Adverse Event

7.2.1 Assessment of Severity

The descriptions and grading scales found in the revised NCI-CTCAE v5.0 will be utilized for AE reporting. A copy of these criteria can be downloaded from the website: https://ctep.cancer.gov/protocoldevelopment/electronic_applications/ctc.htm.

- **Grade 1:** Mild; asymptomatic or mild symptoms; clinical or diagnostic observations only; intervention not indicated
- **Grade 2:** Moderate; minimal, local or noninvasive intervention indicated; limiting age appropriate instrumental activities of daily living (ADL)*
- **Grade 3:** Severe or medically significant but not immediately life-threatening; hospitalization or prolongation of hospitalization indicated; disabling; limiting self-care ADL**
- **Grade 4:** Life-threatening consequences; urgent intervention indicated
- **Grade 5:** Death related to AE

*Instrumental ADL refer to preparing meals, shopping for groceries or clothes, using the telephone, managing money, etc.

** Self-care ADL refer to bathing, dressing and undressing, feeding self, using the toilet, taking medications, and not bedridden.

For AEs not included in the NCI-CTCAE v5.0 grading system, the following guidelines will be used to describe severity.

- **Mild** – Events require minimal or no treatment and do not interfere with the subject's daily activities.
- **Moderate** – Events result in a low level of inconvenience or concern with the therapeutic measures. Moderate events may cause some interference with functioning.
- **Severe** – Events interrupt a participant's usual daily activity and may require systemic drug therapy or other treatment. Severe events may be potentially life-threatening or incapacitating.

NOTE: A distinction should be drawn between serious and severe AEs. Severity is an estimate or measure of the intensity of an AE, while the criteria for serious AEs are indications of adverse subject outcomes for regulatory reporting purposes. A severe AE need not necessarily be considered serious and a serious AE need not be considered severe.

7.2.2 Assessment of Causality

The clinician's assessment of an AE's relationship to IP is part of the documentation process, but it is not a factor in determining what is or is not reported in the study. If there is any doubt as to whether a clinical observation is an AE, the event should be reported. All AEs must have their relationship to IP assessed. In a clinical trial, the IP must always be suspect. To help assess causality, the following guidelines are used.

Related – The AE is known to occur with the IP, there is a reasonable possibility that the IP caused the AE, or there is a temporal relationship between the IP and event. Reasonable possibility means that there is evidence to suggest a causal relationship between the IP and the AE.

Not Related – There is not a reasonable possibility that the administration of IP caused the event, there is no temporal relationship between IP and event onset, or an alternate etiology has been established.

7.2.3 Expectedness

The Sponsor will be responsible for determining whether an AE is expected or unexpected.

- **Unexpected** - An AE will be considered unexpected if the nature, severity, or frequency of the event is not consistent with the safety information Section 6.0 (Guidance for Investigators) of the IB for the IP. "Unexpected," as used in this definition, also refers to AEs or ARs that are mentioned in the IB as occurring with a class of drugs or as anticipated from the pharmacological properties of the drug not specifically mentioned as occurring with the IP under investigation.
- **Expected** - AEs that are common and known to occur for the IP being studied. Expectedness refers to the awareness of AEs previously observed, not on what might be anticipated from the properties of the IP.

7.3 Timing for Event Assessment and Follow-up

All AEs occurring while on study must be documented appropriately regardless of relationship. All AEs will be followed to adequate resolution. The occurrence of an AE or SAE may come to the attention of study personnel during study visits and interviews of a study subject presenting for medical care, or upon review by a study monitor.

Any medical condition that is present at the time that the subject is screened will be considered as baseline and not reported as an AE. However, if the pre-existing condition deteriorates at any time after the subject signs the main study ICF, it will be recorded as an AE. Unanticipated problems will be recorded in the data collection system throughout the study.

AEs characterized as intermittent require documentation of onset and duration of each episode.

7.4 Procedures for Recording and Reporting of Adverse Events

Event	Reporting Procedures
Adverse Event	
Subjects will be followed continuously for AEs during the study and for 90 days after the last dose of IP. After a subject is discontinued from IP due to PD or for other reasons, any ongoing AE should be followed until resolution (or return to baseline) and documented in the eCRF, regardless of whether the event(s) is attributed to trial medication. If another anti-cancer agent is started within 90 days of the last dose of SL-172154, only SAEs and irAEs that occur before the new anticancer therapy should be recorded. The following information will be recorded: description, date of onset and end date, severity, assessment of relatedness to trial medication, and action taken. Follow-up information should be provided as necessary. AEs will be followed either until resolution, or the event is considered stable.
 
It will be left to the Investigator's clinical judgment to decide whether an AE is of sufficient severity to require the subject's removal from treatment. A subject may also voluntarily withdraw from treatment due to what he or she perceives as an intolerable AE. If either of these occurs, the subject must undergo an end of trial assessment and be given appropriate care under medical supervision until symptoms cease, or the condition becomes stable.

Serious Adverse Event	
The study clinician will complete a SAE Form within the following timelines:
 
• All deaths and immediately life-threatening events, whether related or unrelated, will be recorded on the SAE Form and submitted to the study Sponsor or designee within 24 hours of site awareness.• Other SAEs regardless of relationship, will be submitted to the study Sponsor or designee within 24 hours of site awareness. 
All SAEs will be followed until satisfactory resolution or until the site investigator deems the event to be chronic or the adherence to be stable. Other supporting documentation of the event may be requested by the Sponsor and should be provided as soon as possible. The Sponsor will be responsible for notifying Regulatory Authorities of any unexpected fatal or life-threatening suspected AR as soon as possible but in no case later than 7 calendar days after the Sponsor's initial receipt of the information. The Sponsor will be responsible for notifying Regulatory Authorities of any other serious unexpected suspected adverse reaction as soon as possible but in no case later than 15 calendar days after the Sponsor's initial receipt of the information.

Event	Reporting Procedures
	
Sponsor Contact Information for SAE Reporting
 
Email: [REDACTED]
 
eFax number: [REDACTED]

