2. STUDY OBJECTIVES AND OUTCOME MEASURES

Objective	Outcome Measure
Primary Objectives	
To evaluate the safety and tolerability of ITI administration of SL-172154 and to identify the maximum tolerated dose (MTD) or maximum administered dose (MAD) of SL-172154
 
Safety/tolerability outcomes include: incidence of all adverse events (AEs) and immune-related adverse events (irAE), serious adverse events (SAEs), fatal SAEs, dose limiting toxicity (DLT), AEs and irAEs leading to discontinuation, and changes in safety assessments (e.g., laboratory parameters, vital signs etc.) per National Cancer Institute Common Terminology Criteria for Adverse Events (NCI-CTCAE – version 5.0).
 
The MTD is defined based on the rate of DLTs and the MAD is the highest dose administered.

Secondary Objectives	
To select the recommended Phase 2 dose (RP2D) for SL-172154 when administered by intratumoral injection (ITI)
 
Based on review of all data collected during dose escalation and the pharmacodynamic cohort including safety, tolerability, PK, anti-tumor activity, and pharmacodynamic effects
 
To assess preliminary evidence of anti-tumor activity of SL-172154 when administered by ITI
 
Response per investigator assessment according to Response Evaluation Criteria in Solid Tumors version 1.1 (RECIST v1.1).
 
 ▪ Objective response rate (ORR) (proportion of subjects whose best response is a complete response [CR] or partial response [PR]) ▪ Time to response (TTR): time from the first dose until the first response (CR or PR, whichever is recorded first) that is subsequently confirmed ▪ Duration of response (DOR): time between first response (CR or PR, whichever is recorded first) that is subsequently confirmed and date of disease progression ▪ Change from baseline lesion diameter for injected lesion ▪ Change from baseline lesion diameter for non-injected lesion

Objective	Outcome Measure
Secondary Objectives	
To evaluate anti-drug antibodies (ADA) to SL-172154 when administered by ITI during and after treatment.	
 ▪ Number/proportion of subjects with positive ADA titer ▪ ADA duration ▪ Transient vs. persistent ADA

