- n. **AE Monitoring:** Subjects will be followed continuously for AEs during the study and for 90 days after the last dose of SL-172154. After a subject is discontinued from SL-172154, any ongoing AE should be followed until resolution (or return to baseline) and documented in the eCRF. If another anti-cancer agent is started, only SAEs and AEs that occur prior to starting the new anticancer therapy should be recorded. In the event of a continuing AE, the subject will be asked to return for follow-up until the AE has resolved or is deemed to be continuing indefinitely. AEs will be characterized per NCI-CTCAE criteria v5.0 and events recorded in the eCRF.
- o. Ad hoc blood samples for clinical safety labs should be collected for SAE related to injection-related reaction or CRS events as noted in Section [6.3.6.3](#) and the SLM.
- p. **Archival tumor tissue (from a recent biopsy):** Archival tissue, if available, will be collected from **all subjects**. If an inadequate amount of archived tissue is available, the subject may still participate in the study if they meet eligibility criteria for the study. Moreover, archival tissue may be accepted in lieu of the pre-treatment tumor biopsy if the subject has not undergone treatment since time of specimen collection and if the sample was collected via punch biopsy or core needle biopsy and adequate sample is available for analysis. Please notify the sponsor if archival tissue will be used in lieu of a pre-treatment fresh biopsy. Provide formalin-fixed-paraffin-embedded (FFPE) tissue on slides (recommended minimum of 10 slides) or a block of FFPE tissue (the latter is preferred). Refer to **Section 6.6.2.2 and the SLM for details**.

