8.2 Adverse Events

The AE terms on the eCRFs will be mapped to the preferred terms and system organ classes using the Medical Dictionary for Regulatory Activities (MedDRA) version 24.1. Drug-related AEs are defined as AEs with relationship to study treatment being related or possibly related. A worst-case scenario approach will be taken to handle missing data, i.e., AEs with the relationship to study treatment as missing will be counted as drug-related AEs.

An overview summary of AEs will be produced, in which counts and percentages of subjects with any AE, drug-related AEs, DLT, SAEs, drug-related SAEs, fatal AEs, immune related AEs, Grade 3 or 4 AEs, and AEs leading to drug withdrawn, dose not given/held, and dose not completed.

The AE summary tables will use the following algorithms for counting subjects with AEs:

- **Preferred term rows:** each subject is counted once within each unique preferred term at the maximum grade. For example, if a subject has two headaches, the subject is counted only once under the preferred term “Headache”. Subjects experiencing the same AE preferred term several times with different grades will only be counted once with the maximum grade.
- **SOC rows:** each subject is counted only once at the maximum grade at each SOC level although they may have several different preferred term events within the same SOC.
- **Any event row:** each subject with at least one adverse event will be counted only once at the maximum grade no matter how many events they have.

All AEs and drug-related AEs will be summarized by MedDRA system organ class, preferred term and maximum toxicity grade. The non-serious AEs will be summarized by MedDRA system organ class and preferred term. The system organ class and preferred terms will be ordered by descending order of the subject incidence of system organ classes and preferred terms within each system organ class based on all subjects in the analysis population.

The following summary tables will be presented by MedDRA preferred term, in which the preferred terms will be order by descending order of subject incidence of preferred terms based on all subjects in the analysis population.

- Summary of all AEs.
- Summary of drug-related AEs.
- Summary of SAEs.

Listings of all AEs and DLTs will be presented in data listings. Listing of all AEs for the Screen Failures population will be presented in a data listing.

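### Protocol Section 7.4 records only SAEs and irAEs before a new anti-cancer therapy, while Section 7 and the SOA record all AEs, so some non-serious AEs could go unrecorded

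*Protocol*

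**What the plan says.** Three places in the protocol set out what to record when a subject moves to another anti-cancer agent.

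- Section 7.4, in the adverse event row, for an agent started within 90 days of the last dose: "only SAEs and irAEs that occur before the new anticancer therapy should be recorded".
- Section 7, opening paragraph, for the same situation: "only SAEs and AEs that occur prior to starting the new anticancer therapy should be recorded".
- Section 6.1, SOA footnote n, without the 90-day condition: "If another anti-cancer agent is started, only SAEs and AEs that occur prior to starting the new anticancer therapy should be recorded".

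Section 7.3 adds a general rule: "All AEs occurring while on study must be documented appropriately regardless of relationship". Section 7.4 itself opens with full follow-up: "Subjects will be followed continuously for AEs during the study and for 90 days after the last dose of IP".

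On the analysis side, the primary outcome in Protocol Section 2 starts from the "incidence of all adverse events (AEs) and immune-related adverse events (irAE), serious adverse events (SAEs" and continues through further safety measures. SAP Section 8.2 plans an overview with "counts and percentages of subjects with any AE, drug-related AEs, DLT, SAEs, drug-related SAEs, fatal AEs, immune related AEs" and further categories, and states: "The non-serious AEs will be summarized by MedDRA system organ class and preferred term".

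**The concern.** An AE that is neither serious nor labelled immune-related, and that occurs before the new agent, is recorded under Section 7 and footnote n but not under Section 7.4. The narrower rule is not in a minor place. Section 7 ends by sending the reader to 7.4 for documentation and reporting, and Section 6.9 also points there. A site that follows those references meets the narrower instruction, while a site working from the SOA meets the wider one.

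The situation is foreseeable. Treatment runs in principle until progression (Section 3.13), and both Section 3.14 and the SOA footnote on the post-treatment visit anticipate a following therapy.

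At stake is the completeness of a primary outcome that covers all AEs, and of the SAP table reserved for non-serious AEs (Table 14.3.1.8), which is the class that 7.4 would partly drop. Section 3.5 also allows Grade 3 or higher AEs after day 21 to be weighed in choosing the RP2D. A non-serious Grade 3 event not called immune-related could be missing from that review. An event that was never entered cannot be restored by an analysis rule.

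**Working it through.** The plan gives no figure for this point, so there is none to reproduce. The check is a comparison of the rules, a search for text that settles the difference, and a simple scale.

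**Step 1. Which events are treated differently.** Take a subject who starts a new agent within 90 days of the last dose.

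| Event before the new agent | Section 7 and footnote n | Section 7.4 |
|---|---|---|
| SAE, including fatal | recorded | recorded |
| Non-serious irAE | recorded | recorded |
| Non-serious AE, not immune-related | recorded | not recorded |

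Events that begin after the new agent starts are not recorded under either rule. The dispute is confined to the last row.

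**Step 2. Which period is exposed.** Section 7.4 can be read as limiting everything before the new therapy, or only the stretch from last dose to new therapy. The first reading clashes with the opening sentence of 7.4, so the second is the more natural. Both conflict with Section 7 and footnote n.

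**Step 3. Whether anything resolves it.** The protocol gives no order of precedence between sections. The Amendment 01 summary does not mention the matter. SAP Section 8.2 defines neither a treatment-emergent window nor a cut at new anti-cancer therapy.

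**Step 4. Which outputs can move.**

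- Can be too low: counts by preferred term and system organ class, drug-related AEs, non-serious AEs, Grade 3 or 4 AEs.
- Any AE: changes only if the subject has no other recorded AE.
- Unchanged: SAEs, fatal SAEs, irAEs.
- Little affected: the DLT and MTD evaluation, which rests on the first 21 days.

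**Step 5. Scale.** Inputs: planned N of about 18 and cohorts of about 3 (Protocol Section 9.1). If a subject had a given term only in the exposed window, losing that event lowers the term's incidence by 1/n, where n is the denominator:

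- all subjects at planned N: 1/18 = 0.056, or 5.6 percentage points;
- one cohort of 3: 1/3 = 0.333, or 33 percentage points.

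If k subjects are affected for the same term, the overall change at planned N is k × 5.6 points. The documents do not give k, and k = 0 gives no change. SAP Section 1 says that enrollment was stopped early. If fewer than 18 were treated, the overall change per affected subject is larger than 5.6 points.

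**The case against.** The strongest reply is that little would be lost in practice. Section 7 asks for all observed or volunteered AEs, serious or not, and Section 7.3 says much the same. Recording is continuous, so a site will usually have entered an event before it knows that a new agent is coming, and nothing tells sites to delete entries. The post-treatment visit falls within 30 days of the last dose and before any new therapy. Section 3.7 tells investigators to treat events without a clear alternative cause as potentially immune-related, which widens the class that 7.4 keeps.

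Most of this stands as a limit on size. It does not remove the conflict. Sections 7 and 7.3 are part of the contradiction and do not settle it. The Section 3.7 advice concerns events thought to be treatment-related, so it narrows the gap without closing it, and it makes recording under 7.4 depend on an investigator's label.

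A reader might infer more than the documents support:

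- That the loss falls on subjects who stop drug early. The rule is triggered by a new agent within 90 days of the last dose, after any length of treatment.
- That recording does differ between sites. Two conflicting instructions make this possible, but nothing in the documents shows it.
- That 90 days of follow-up are lost per subject. Ninety days is the outer bound. The disputed period ends when the new therapy starts.

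**Conclusion.** The contradiction is real, sits in current text and is not resolved elsewhere. Section 7.4 as written would leave out non-serious, non-immune-related AEs that the primary outcome is meant to count, mainly those between last dose and new therapy.

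It would be tempting to conclude that the primary AE incidence as a whole depends on which section a site reads. That goes too far, because SAE, fatal SAE and irAE counts are the same either way, and the any-AE figure moves only for a subject with no other recorded AE.

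The 5.6-point and 33-point figures are ceilings per affected subject. They assume the planned N of 18 or exactly 3 subjects in the denominator, and a term that the subject had only in the exposed window. With an unknown number of affected subjects, the lower bound is zero. This is a fault in a data-collection instruction with a limited and unquantified effect, and it is cheap enough to correct that it should be corrected.

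**What to change.** 1. In Protocol Section 7.4, change SAEs and irAEs to SAEs and AEs, in line with Section 7 and footnote n. In the same edit, make the 90-day condition the same in all three places, since footnote n omits it.
2. Send sites a short clarification. Because enrollment has already stopped, a change of protocol wording alone will not recover events that were left out.
3. Before database freeze, identify every subject who began another anti-cancer therapy within 90 days of the last dose, and check against source that AEs before that therapy were entered in the eCRF.
4. State the same AE inclusion window, with its cut at new anti-cancer therapy, in SAP Section 8.2.

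The cost is a one-word correction, a letter, a targeted check in a trial planned for about 18 subjects, and a sentence or two in the SAP. No sample size or analysis method changes.
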